1.0 PROJECT SUMMARY

Frailty is a comprehensive measure of health status that describes the vulnerability of a person to health stressors (1–4). Frailty is measured along a continuum from '*managing well*' to '*severely frail*', and is characterized by progressive impairment in activities of daily living (4). More than one out of every four patients with Chronic Obstructive Pulmonary Disease (COPD) are frail, and frailty is associated with frequent exacerbations, hospital readmission, mortality, and poor quality of life (3,5–10). Further, intervening with specialized exercise, nutritional, and personal supportive care programs has the potential to reverse, or stabilize frailty when identified at the earlier stages (2,3,7).

However, little is known about whether frailty measurements can be used to predict the risk of deteriorations in validated patient-reported outcomes, if frailty measurements are reproducible among patients with COPD, and if patient care preferences differ between degrees of frailty. Further, it is unknown whether frailty categories could be used to guide tailored interventions to address and manage frailty, and whether frailty-focused interventions could improve long term outcomes in addition to conventional treatments (6,10).

We hypothesize that progressive degrees of frailty will reliably predict important deteriorations in patient-centered outcomes over time, including health-related quality of life, symptom burden, psychosocial wellbeing, and measures of survival and health service use.

If this association between frailty and health is confirmed, then it follows that frailty could be used as a risk stratification tool to guide tailored interventions for population subgroups with varying degrees of frailty.

To inform the development and testing of effective care interventions within categories of frailty, the following questions must first be addressed:(1) What is the predictive value of progressive degrees of frailty on deterioration in patient-centered outcomes and increased health care utilization among people with COPD? (2) What are the differences in expectations of clinical care between patients and physicians within different degrees of frailty? (3) What is the inter-rater agreement between patients and physicians who use the Clinical Frailty Scale (CFS) to measure frailty? (4) What is the test-retest reliability of the CFS when used by the same patient at 2 different time-points, 6 months apart?

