2.0 BACKGROUND

What is the Problem to be Addressed? Patients with Chronic Obstructive Pulmonary Disease (COPD) feel that their needs are not met within the current healthcare system (11). In a scoping review of a decade's worth of qualitative evidence, patients with COPD reported feeling poorly informed about their condition, vulnerable when hospitalized, unconfident in community based services, and lacked an understanding of their disease

trajectory and significance of their exacerbations (11). Most importantly, patients reported that their subjective distress seemed *invisible* to clinicians who tended to focus on objective health indicators, and that clinicians infrequently addressed or referred patients for assistance with their substantial non-medical needs (7).

From a health system perspective, COPD exacerbations are a leading cause of hospitalizations and re-admissions in Canada, and cost our health system over 700 million dollars annually (12,13). In a closer review of hospital-related costs for COPD care, the highest costs were incurred by patients with acute illness, but also by *frail* patients who developed significant functional limitations and could not return home (14).

Both the patient and health system perspectives suggest that our current paradigm for COPD care in Canada is not optimal. While health providers focus on COPD-specific metrics, which have been correlated with future risk of mortality and hospitalization (15–17), clinicians lack appropriate evidence based tools to evaluate the non-pulmonary complications of COPD and overall wellbeing of these patients (18).

In this setting, there is a need for innovative care approaches which (1) reliably predict the outcomes that are important to patients living with COPD, (2) are easily implemented in the health system, and (3) have a direct impact on front line COPD management across health care settings. Care models which incorporate assessments of '*Frailty*' may provide this desired innovative approach to enhance patient-centered COPD care. There are currently no studies to determine whether health providers could use measurements of frailty to accurately predict current and future decline in patient-centered outcomes, and whether patients' expectations of healthcare change between different degrees of frailty.

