3.0 OBJECTIVES

The aim of this research program is to evaluate *frailty* measurements as a risk stratification tool to predict deteriorations in patient-reported outcomes, to gain a better understanding of patient and physician preferences for care within varying degrees of frailty, and to assess the change of frailty measurements over time. More specifically, our study objectives are:

1. To determine the predictive value of progressive degrees of frailty on deterioration in patient-centered outcomes and increased health care utilization among people with COPD, after adjustment for important clinical factors including age, sex, comorbidity, home support, number of medications, pulmonary rehabilitation, lung function, dyspnea, and exacerbation history.
2. To describe the differences in expectations of clinical care between physicians and patients within different degrees of frailty.
3. Determine the inter-rater agreement between patients and physicians who use the Clinical Frailty Scale (CFS) to measure frailty.

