5.5 Data collection methods

5.5.1 *Patient Self-Assessed Frailty*: Patients will use the CFS to self-assess frailty at their clinical baseline, which measures nine distinct degrees of frailty from ‘managing well’ to ‘terminally ill’ (**Figure 1**). The wording in the CFS has been adapted and validated for patient-use (32).

5.5.2 *Patient Expectations of Health Care*: Patients will review and rank items on a standardized list of care interventions (i.e. pulmonary exercise programs, homecare, self-management education). The study team developed the list based on services recommended in Health Quality Ontario’s updated ‘Quality Standards for COPD’ document (38), and currently available community-based programs to help individuals with their functional, social, and lung health needs. The document will be written in lay language and a member of the research team will ensure items on the list are well understood by patient participants. Patient participants will rank each item on a likert scale from 1 (least important), to 5 (most important), to indicate their care preferences. ([COPD & Frailty - Baseline survey](#))

5.5.3 *Patient Baseline Health Data* (see **Data Collection Sheet – Baseline visit)**: We will collect variables from direct patient assessment and review of the electronic medical record at the time of recruitment:

- Socio-Demographic Data (age, sex, body mass index, physician-assessed clinical frailty scale score, current dwelling, caregiver support, marital status, education level, type of home assistance services, and duration of time since initial diagnosis).

- COPD-Specific Factors (Spirometry values (FEV1, FVC, FEV1/FVC), smoking history in pack-years, home-oxygen use, 6-minute walk test distance (if available), influenza and pneumococcal vaccination status, use of pulmonary rehabilitation, and number of flare-ups in the last year).
- General Health Data (co-morbidities, presence of family physician).
- Previous Health Service Utilization (hospitalizations, intensive care unit admissions, emergency room visits in last 1-year).

5.5.4 **Physician Data Collection:** We will ask the referring respirologist (in the patient's circle of care) to provide a frailty measurement at the time of study enrolment, using the CFS (Figure 1). This physician will also rank their desired care interventions for the patient using the same standardized list given to study participants (see [Recruitment Survey](#)).

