5.7.1 ***Quantitative Analysis (Objective 1):*** The primary outcome (HRQOL using SGRQ-C scores) will be analyzed using multiple variable linear regression, with degree of frailty as the main predictor ('vulnerable', 'mildly frail', 'moderately frail', and 'severely/very severely frail'). Secondary outcomes for symptom burden (CAT and mMRC scales) and psycho-social wellbeing (GAD-7 and PHQ-9) will be described with median (IQR) statistics within each degree of frailty and analyzed with multiple variable linear regression to determine their associations with progressive degrees of frailty. Finally, the association between frailty and health service utilization (hospitalization, emergency room visit) and mortality will be analyzed with multivariable logistic regression. Potential confounding variables will be selected a-priori and forced into the model, regardless of statistical significance. Backwards selection will be used to obtain the most parsimonious model.

5.7.2 ***Quantitative Analysis (Objective 2):*** We will use descriptive statistics (proportions, means \pm SD, medians (IQR)) to characterize the ranked care expectations, socio-demographic, and disease-specific, variables. Variables will be stratified by physician-assessed degrees of frailty, and chi-square and ANOVA testing will be used to analyze differences in variables across degrees of frailty, for categorical and continuous variables, respectively.

5.7.3 ***Quantitative Analysis (Objective 3 & 4):*** We will calculate the percentage of agreement to assess inter-rater agreement between patients' self-assessed and physician-assessed frailty ratings at the baseline visit. This will be presented as a

cross-tabulation table. We will graph the trajectory of frailty rating between baseline, 6-month, and 12-month visits for the study cohort.

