9.0 EXPECTED IMPACT OF THIS WORK

Our study will inform several aspects of care for patients with COPD: a) the validity of frailty assessments as a long-term predictor of patient-centered outcomes; b) the reliability and accuracy of the assessments of frailty, c) the patient's preferences of care according to the different levels of frailty; and d) any potential differences in the perception of frailty between patients and physicians and whether this may have a potential impact on clinical outcomes. We believe that these results will facilitate a practice change to introduce frailty measurements as a risk stratification tool for health providers (and patients), and to enhance personalized care according to patient preferences. This study will provide important context for our next steps to design and test the impact of personalized, patient-centered care interventions in subgroups of frail patients with chronic lung disease.

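### Objective 2 asks how patients and their own physicians differ, but section 5.7.2 names no paired patient-physician estimate

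*Combined protocol and SAP*

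**What the plan says.** Section 3.0 gives Objective 2 as: "To describe the differences in expectations of clinical care between physicians and patients within different degrees of frailty". The second research question in section 1.0 is the same contrast: "What are the differences in expectations of clinical care between patients and physicians within different degrees of frailty".

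The data for it are paired. Section 5.5.2 says: "Patient participants will rank each item on a likert scale from 1 (least important), to 5 (most important". Section 5.5.4 says of the referring respirologist: "This physician will also rank their desired care interventions for the patient using the same standardized list given to study participants". Section 5.8 confirms the physician half. The patient half rests on 5.5.2.

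Section 5.7.2, the analysis for Objective 2, plans proportions, means with SD and medians with IQR for the ranked expectations and other variables, stratified by physician-assessed frailty. It then states that "chi-square and ANOVA testing will be used to analyze differences in variables across degrees of frailty". No section names a patient-physician difference, a concordance measure or a contrast between raters for the care items.

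For Objective 3, section 5.7.3 plans the percentage of agreement between the two baseline CFS ratings, shown as a cross-tabulation.

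**The concern.** The objective compares two raters inside a frailty stratum. The only tests in 5.7.2 compare frailty strata with each other. A report that followed the section to the letter could show how expectations vary with frailty and still give no stated estimate of how far patients and their own physicians are apart, which is what Objective 2 asks. The pairing is the main strength of these data for that question, and nothing in 5.7.2 uses it.

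**Working it through.** **Inputs.** From the documents: at least 30 patients in each of four frailty categories, 120 in all (5.4); seven respirologists (5.1); patient scores of 1 to 5 (5.5.2). Assumed: physicians use the same 1 to 5 scale (stated only for patients), and the strata of 5.7.2 are the four categories of 5.4 with 30 pairs each. The documents give no rating data, so every table below is hypothetical.

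**The plan's own figures.** None is given for Objective 2 or 3. The sample sizes in Appendix 1 reproduce (noncentral F, 10 and N-11 df, noncentrality f² x N: N = 84, power 0.8040; N = 64, power 0.8014), but they belong to Objective 1 and do not bear on this point.

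**1. What the across-strata tests can see.** For one rater and one item, F is the between-strata mean square over the within-strata mean square. Add a constant to all of one rater's scores: every stratum mean and the overall mean move by that constant, so all deviations, and F, stay the same. As an illustration, take 4 strata of 30, a shared patient component and independent rater errors (SD 0.7 each), scores rounded to 1-5, physicians about 0.48 points higher in every stratum, and 4,000 runs. ANOVA across strata rejects in 5.1% of runs for patient scores and 4.9% for physician scores, which is the alpha level. A paired contrast over the 120 pairs rejects in 99.9%.

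**2. What tables by rater can see, equal averages.** Rows are patient scores 1-5, columns physician scores 1-5, n = 30. Both tables have margins 3, 6, 9, 8, 4 for both raters: mean 3.13, SD 1.20, median 3 (IQR 2 to 4).

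- Table A: 1,0,1,1,0 / 0,1,2,2,1 / 1,2,3,2,1 / 1,2,2,2,1 / 0,1,1,1,1. Correlation 0.06; 22 of 30 pairs differ, 12 by 2 or more points.
- Table B: 1,1,1,0,0 / 1,2,2,1,0 / 1,2,3,3,0 / 0,1,2,3,2 / 0,0,1,1,2. Correlation 0.59; 19 of 30 differ, 5 by 2 or more points.

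The side-by-side summaries are identical. The within-pair disagreement is not.

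**3. Unequal averages.** Patient margins 7, 9, 8, 4, 2 (mean 2.50) and physician margins 3, 6, 9, 8, 4 (mean 3.13) give a difference of -0.63. Both SDs are 1.196. The variance of the paired difference is s1² + s2² - 2 r s1 s2.

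- Table C: 1,1,2,2,1 / 1,2,3,2,1 / 1,2,2,2,1 / 0,1,1,1,1 / 0,0,1,1,0. r = 0.10, SD of the difference 1.61, half-width t(29) x 1.61/sqrt(30) = 0.60, 95% CI -1.23 to -0.03.
- Table D: 2,3,2,0,0 / 1,2,3,2,1 / 0,1,3,3,1 / 0,0,1,2,1 / 0,0,0,1,1. r = 0.63, SD of the difference 1.03, half-width 0.39, 95% CI -1.02 to -0.25.

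From the two separate summaries a reader can only form t(58) x sqrt((1.196² + 1.196²)/30) = 0.62, the same in both cases.

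**4. Precision to expect.** With an assumed SD of the difference of 0.8 to 1.5, 1.96 x SD/sqrt(30) gives half-widths of 0.29 to 0.54 points per item and stratum.

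**5. Clustering by respirologist.** The design effect is 1 + (m-1) x ICC, with an assumed ICC of 0.02 to 0.10 and equal caseloads. In a stratum m = 30/7, giving 1.07 to 1.33, so intervals should be 3% to 15% wider. For the whole cohort m = 120/7, giving 1.32 to 2.61, so 15% to 62% wider.

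**6. Objective 3.** Rows are physician levels 4-7 (30 each), columns patient levels 4-7.

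- Balanced near misses: 20,10,0,0 / 10,10,10,0 / 0,10,10,10 / 0,0,10,20.
- All disagreements patient-lower: 30,0,0,0 / 20,10,0,0 / 0,20,10,0 / 0,0,20,10.
- Half of the disagreements three levels apart: 15,0,0,15 / 0,15,15,0 / 0,15,15,0 / 15,0,0,15.

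All have 60/120 agreement (Wilson 95% CI 41% to 59%). Quadratic-weighted kappa is 0.80, 0.80 and 0.00; the mean signed difference is 0.00, -0.50 and 0.00. Moving three (4,4) pairs of the balanced table to (4,9) lowers weighted kappa from 0.80 to 0.59; leaving those pairs out gives 0.79.

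**7. A caution on the signed difference.** Section 5.4 does not say whose rating fills the quotas. Suppose it is the physician's, with 30 patients at each of levels 4, 5, 6 and 7-8. Assume true frailty with mean 3.5 to 4.5 and SD 1.3, and two unbiased raters with error SD 0.5. The simulated patient-minus-physician difference is about -0.17 to -0.34 overall and -0.45 to -0.60 in the most severe group. Without quota selection it is 0.00.

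**The case against.** The objective is to describe, and in 5.7.2 the stratified descriptive statistics, not the tests, carry it. Both raters' expectations are collected, so patient and physician columns within each stratum are a natural reading, and a gap in averages would then be visible. This stands. A reader might infer that Objective 2 has no analysis at all, or that it needs a hypothesis test; the documents support neither. The paired records are also kept, so the estimate can be added at analysis. What survives is narrower: the section names no patient-physician estimate, and rater-by-rater summaries lose the pairing.

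The across-frailty tests are not a mistake either. The protocol separately asks "if patient care preferences differ between degrees of frailty" (1.0), whether patients' "expectations of healthcare change between different degrees of frailty" (2.0), and expects to inform "preferences of care according to the different levels of frailty" (9.0). The tests suit that question.

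On Objective 3, a reader might infer that percent agreement makes the plan deficient. It does not: the cross-tabulation keeps distance and direction, and the other summaries can be derived from it. Weighted kappa also depends on the frailty mix. One fixed error pattern (50% exact, 25% one level lower, 25% one level higher) gives 0.83 with 30 at each of levels 4 to 7, 0.76 with 60/36/18/6 and 0.62 with 80/30/10. Leaving out level 9 is contestable: section 2.0 treats the CFS as ordinal over all nine levels, while Figure 1 reserves level 9 for people who are dying but show no other clear frailty.

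Finally, under 5.3 the physician rates at the clinic visit and the patient around a later baseline telephone visit. A paired difference therefore mixes disagreement with elapsed time. That stands as a limitation.

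**Conclusion.** The point holds as a cheap improvement to a descriptive, non-primary objective. Section 5.7.2 tests only across degrees of frailty and names no patient-physician estimate. Those tests cannot show a gap that is constant across strata, and tables by rater would show neither within-pair disagreement nor the precision of a gap. That marginal summaries do not determine paired disagreement is general. The sizes shown (12 against 5 pairs at least 2 points apart; half-width 0.60 against 0.39) rest on hypothetical tables, 30 pairs per stratum and a shared 1 to 5 scale. The primary analysis is not affected.

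The Objective 3 additions are optional. If a signed CFS difference is reported, a reader might take a negative value as patients under-perceiving their frailty. The documents do not support that inference unaided: if the quotas are filled on the physician rating, regression to the mean can produce it when neither rater is biased.

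**What to change.** **Section 5.7.2.** Keep the across-frailty analysis. Add, for each care item within each physician-rated stratum, the paired patient-minus-physician difference with a 95% CI and the share of pairs that differ, labelled as descriptive estimates. State that physicians use the same 1 to 5 scale. If they do not, report within-pair concordance on a common ordering of the items instead. Give two limitations: seven respirologists supply the physician ratings, so intervals that treat pairs as independent are too narrow; and the two ratings are made at different times.

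**Section 5.7.3, optional.** Add a 95% CI to percent agreement and, if wanted, a weighted kappa read beside the cross-tabulation and shown with and without ratings of 9. Report a signed CFS difference only with the warning about quota selection.

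**Cost.** Analysis-plan wording and a modest amount of extra analysis on data already collected, with no added patients, visits or instruments. The downside is several per-item intervals from about 30 pairs each, which will be fairly wide.

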5.8 Data sources

- **Patient surveys:** For each study visit, patients will be asked to complete surveys relating to: CFS, SGRQ-C, mMRC Dyspnea Scale, CAT, GAD-7 and PHQ-9 .
- **Physician surveys:** CFS and care expectations for patient at time of enrolment
- **Electronic Medical Record:** Baseline health data, socio-demographic data, COPD-specific data, previous health care service utilization (1 year prior to study enrolment)
- **Baseline telephone visit with research team:** baseline health data, COPD specific data, previous health care service utilization.
- **6 & 12 month telephone visits with research team:** CFS, change in health status (stress event or falls) since last visit.

6.0 STUDY TIMELINE

- **Pre-implementation & Education of study staff and co-investigators** (December 2019 – February 2020):
 - Research Ethics Board application and study set-up
 - Prepare study documents (patient information sheets, physician reminders, poster of CFS) to increase awareness and reminder to enroll patients
 - Host session with respirologists from TOH General Campus to review how to use the CFS, review study process, and research plan
- **Hire** (February-April 2020):
 - Hire research assistant to assist with the collection of data.
 - Acquire equipment necessary for the study conduct (iPad, study laptop).
- **Implementation & Data Collection** (November 2022- March 2024):
 - Recruit patients from the Respirology outpatient clinic of TOH, General campus, obtain consent (November 2022 to March 2024)
 - Collect patient data (at baseline, 6 months, and 12-month follow-ups) with study staff.
- **Data Analysis** (March 2024):

- Quantitative data analysis performed by an OHRI methodologist from the Ottawa Hospital Performance Measurement team.
- **Knowledge Translation & Next Steps** (April 2024 and beyond):
 - Manuscript submissions and plan for next steps

7.0 DATA MANAGEMENT

The data collected will be password protected and will not leave TOH. Only study personnel will have access to the study data. A study master list (containing MRN and patient name) will be linked to a study ID. This master linking file will be kept separate from the main study dataset in a protected folder on a secure TOH sever. Only the unique study ID will be used on the patient surveys and study case report forms. The study files will not be stored on the hard drives of portable devices or on USB keys.

8.0 CHALLENGES AND MITIGATION STRATEGIES

8.1 Patient Recruitment & Transportation: We may experience difficulty recruiting patients who are severely frail. However, we have chosen The Ottawa Hospital ambulatory care clinic as a referral base, where the level of staff engagement for research is high, and patient volume is adequate. To ensure adequate recruitment in the higher degrees of frailty, we have grouped the 'severe' and 'very severe' categories together. Since patients will not require to be on site for study visits, we believe that this will help with participation.

8.2 Study Adherence: We will provide a \$20 coffee gift card incentive for patients to attend the initial study visit, 6 month visit, 12-month visit. This is intended to improve adherence to the study protocol and mitigate losses to follow up. Enrolled patient participants will receive personalized communication from the study coordinator to increase their engagement and participation in the study.

8.3 Patient Participation: While frailty is a widely accepted medical construct that is frequently used by health professionals to describe health status, the term 'frailty' may be associated with negative perceptions from the patient perspective (37,55). We anticipate that patients may feel stigma attached to using the frailty construct to describe their health and may decline to participate as a result. To mitigate this potential challenge, the initial introduction and consent for the study will be done by the patient's respirology circle of care (respirologist or nurse), with whom they have a therapeutic alliance. We will also ensure the use of impartial language during the study visits to enhance patient comfort-level.

